**3.6 Exclusion Criteria**

- 3.6.1 Ongoing or planned concurrent participation in any clinical study involving Investigational Product that has not been approved by the European Medicines Agency for any indication
- 3.6.2 Ongoing or planned concurrent participation in any clinical study where the dosing of Vectibix® is determined by the protocol (participation in clinical trials on an approved drug and observational trials are permitted but these cannot mandate how mCRC should be treated)

**3.7 Subject Enrolment**

All subjects or legally acceptable representatives must personally sign and date the consent form before enrolment, where consent is required. A subject is considered as enrolled upon completion of this requirement. All subjects who enter into the study will be allocated a unique subject identification number. This number will be used to identify the subject throughout the study and must be used on all study documentation related to that subject. The subject identification number must remain constant throughout the entire study. Investigators will be expected to maintain a log of all potential study candidates that includes limited information about the potential candidate including reason for subjects not being enrolled (eg, subject ineligible or refused to participate).

**3.8 Concomitant Therapy**

Throughout the study, investigators may prescribe any concomitant medications or treatments deemed necessary to provide adequate supportive care. There are no proscribed therapies and investigators may treat their subjects according to clinical practice.

**4. STUDY PROCEDURES**

This study is non-interventional and will not alter the clinical management of subjects. No clinic visits other than those routinely scheduled will be required. Data to be recorded on the eCRF should be taken from clinical records collected in the course of normal clinical practice. No additional procedures other than those in line with routine standard of care will be performed and all medical data collected for the study are expected to be a part of standard medical records.

The investigator at each centre is responsible for ensuring that all required data is recorded.

Participating centres will assess the eligibility of patients visiting their clinic against the protocol inclusion exclusion criteria, any eligible subjects may be invited to participate in the study. After informed consent is obtained, where applicable by local law,

---

retrospective data will be collected from Baseline (which occurs prior to the first dose of Vectibix®) up to the point of enrolment. All subsequent chemotherapy cycles and Vectibix® doses will be recorded prospectively.

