## 3. STUDY DESIGN

This is a multicenter, observational, prospective cohort study in France and Germany.

All treatment centres (inpatient and outpatient) with a focus on treating subjects with mCRC in participating countries will be prospectively defined for potential inclusion in the study. Centres will be selected to represent academic, oncology, specialist and private settings, and to provide geographical diversity within each country. A subject log will be maintained and details of all patients not enrolled will be recorded, as permitted by local regulations, including reason for non-enrolment.

Subjects with wild-type *KRAS* mCRC receiving Vectibix® treatment in combination with chemotherapy as first-line treatment in combination with FOLFOX or second-line treatment in combination with FOLFIRI in patients who have received first-line fluoropyrimidine-based chemotherapy (excluding irinotecan) will be eligible for entry to the study.

Enrolled subjects must have received at least one infusion of Vectibix® in combination with chemotherapy a maximum of 42 days before entering study. Retrospective data will be collected from Baseline (which occurs prior to the first dose of Vectibix®) up to the

---

point of enrolment. Subsequent chemotherapy cycles and Vectibix® doses will be recorded prospectively.

Each subject will have data collected until approximately 30 days after the end of Vectibix® treatment, death, withdrawal of consent, loss to follow-up, or up to 12 months from the first dose of Vectibix®, whichever occurs first.

Data will be obtained from routine clinical records and transcribed onto an electronic case report form (eCRF) which will be in three parts:

- (i) Baseline visit
- (ii) Follow-up visit – or next patient visit throughout the observation period based on physician preference for follow up.
- (iii) End of observation– approximately 30 days after the end of Vectibix® treatment or 12 months from the initiation of Vectibix®, whichever occurs first (unless preceded by subject death, loss to follow up or withdrawal of consent).

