### **3.5 Inclusion Criteria**

- 3.5.1 Subject is ≥18 years of age at date of enrolment
- 3.5.2 Histologically or cytologically confirmed carcinoma of colon or rectum
- 3.5.3 Subject with metastatic carcinoma of colon or rectum
- 3.5.4 Confirmed wild-type KRAS status of tumour
- 3.5.5 Subjects whose care will be managed primarily by the enrolling physician and/or all records will be available
- 3.5.6 Tumour assessment (ie, CT/MRI) within 12 weeks (84 days) prior to first Vectibix® infusion
- 3.5.7 Subjects treated with at least one infusion of Vectibix® in combination with chemotherapy a maximum of 42 days before entering study: first-line in combination with FOLFOX or second-line in combination with FOLFIRI in subjects who have received first-line fluoropyrimidine-based chemotherapy (excluding irinotecan) for treatment of wild-type KRAS mCRC per approved prescribing information
- 3.5.8 Subject or subject's legally acceptable representative has provided informed consent (for countries where required per local regulations)

---

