### **4.3 Internal Validity of Study Design**

#### **4.3.1 Selection Bias**

We do anticipate some degree of selection bias within our study. Since we are not recruiting patients until they have been dosed with Vectibix® at least once, there is a

small group of patients who we will not be sampling ie, those who do not commence treatment, or cease treatment very soon after the first dose, usually because of death or disease progression. Therefore the response rate may be inflated slightly and other collected data impacted. Note that in Germany we may only be able to obtain limited data from deceased patients. However generally for most patients this will not limit inclusion of patient data into the study as the study is mainly prospective in design and patients will be alive at study enrolment (where consent is required). Should subjects die during the course of the study it may become more difficult to obtain complete follow up information if the notes are then subsequently filed elsewhere and we need informed consent to obtain them.

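### Centres may choose which eligible subjects to invite once the early course on Vectibix can be known, so treatment-pattern and response estimates could be biased by an unknown amount

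*Protocol*

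**What the plan says.** Protocol Section 4 has centres check patients who attend against the entry criteria, and then says that "any eligible subjects may be invited to participate in the study". Criterion 3.5.7 requires at least one infusion of Vectibix with chemotherapy, given "a maximum of 42 days before entering study". The period before entry is reconstructed from records: "retrospective data will be collected from Baseline (which occurs prior to the first dose of Vectibix®) up to the point of enrolment". Section 3.2 caps enrolment at 350 in France and 390 in Germany.

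Four places bear on selection:

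- Section 4.3.1 expects some bias from missing "those who do not commence treatment, or cease treatment very soon after the first dose, usually because of death or disease progression", and concludes: "Therefore the response rate may be inflated slightly and other collected data impacted".
- Section 3 states: "A subject log will be maintained and details of all patients not enrolled will be recorded, as permitted by local regulations". The reason for non-enrolment is to be included.
- Section 3.7 adds: "Investigators will be expected to maintain a log of all potential study candidates". Its example reasons are ineligibility and refusal.
- Section 6 names centre refusals and patient refusals as the limitations of subject selection, and undertakes to review them and qualify the results if they are appreciable.

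No section requires that every eligible subject be invited, or that subjects be invited consecutively.

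**The concern.** The person deciding whom to approach will usually be the treating physician (criterion 3.5.5) and can already know how the first weeks went. Early delays, dose reductions and stopping are part of the primary outcomes in Section 5.2.1. If subjects with a difficult start are approached less often, those proportions fall and the response rate rises.

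Section 2.3 says the study is meant to show reimbursement bodies how Vectibix is used in real life. Section 5.3 sizes it purely on the width of confidence intervals. Those intervals cover sampling error only, and neither a larger sample nor a later analysis recovers eligible patients who were never approached. A subject who had one infusion and then stopped still meets 3.5.7 and counts as exposed under Section 5.6.2.1, so leaving such subjects out removes part of the target population.

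**Working it through.** **Coverage of the existing safeguards.** The relevant case is an eligible, reachable patient whom the physician does not approach.

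- Section 4.3.1 concerns patients lost because recruitment starts after dosing. It does not consider choice among patients who can be reached.
- Section 6 concerns refusals. A patient who was never asked has not refused.
- The logs in Sections 3 and 3.7 would list this patient as not enrolled. They neither require the invitation nor name non-invitation as a reason, and the only stated follow-up is the refusal review.

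**The Protocol's own precision.** The Wald half-width is 1.96 × √(p(1−p)/n).

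- France, n = 350, p = 0.3: 1.96 × √(0.21/350) = 4.8 points.
- Germany, n = 390, p = 0.3: 1.96 × √(0.21/390) = 4.5 points.

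Both agree with Table 1, as do the whole-country entries for p = 0.1 (3.1 and 3.0) and p = 0.5 (5.2 and 5.0).

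**Hypothetical effect of selective invitation.** Let q be the true proportion with a pattern, and r the invitation rate of subjects with the pattern relative to those without it. The Protocol gives no value of r, so the range 0.9 to 0.5 is an assumption. The expected observed proportion is qr / (qr + 1 − q). For q = 0.3 and r = 0.8 this is 0.24 / (0.24 + 0.70) = 25.5%, a shift of −4.5 points.

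| r | q = 10% | q = 30% | q = 50% |
|---|---|---|---|
| 0.9 | 9.1 (−0.9) | 27.8 (−2.2) | 47.4 (−2.6) |
| 0.8 | 8.2 (−1.8) | 25.5 (−4.5) | 44.4 (−5.6) |
| 0.7 | 7.2 (−2.8) | 23.1 (−6.9) | 41.2 (−8.8) |
| 0.5 | 5.3 (−4.7) | 17.6 (−12.4) | 33.3 (−16.7) |
| Half-width, France / Germany | 3.1 / 3.0 | 4.8 / 4.5 | 5.2 / 5.0 |

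The shift equals the half-width at r of about 0.66 (France) and 0.68 (Germany) for q = 10%, 0.79 and 0.80 for q = 30%, and 0.81 and 0.82 for q = 50%.

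**Where the effect is diluted.** The table treats everyone with the pattern as under-invited. Only what is visible at invitation can be selected on, whereas Section 5.6.2.1 summarises discontinuation over the whole observation period. Assume, since the Protocol gives no figure, that 70% discontinue by 12 months, 15 points of it before invitation. Only those 15 points carry r:

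(0.15r + 0.55) / (0.15r + 0.85)

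This gives 69.5%, 69.1%, 68.6% and 67.6% for r = 0.9, 0.8, 0.7 and 0.5. The shifts of 0.5, 0.9, 1.4 and 2.4 points are all below the half-width at p = 0.7 (4.8 and 4.5, as for p = 0.3).

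**Response.** Take the 57% that Section 2.2.2 reports for panitumumab with FOLFOX. If non-responders were invited 0.8 times as often, the expected value is 0.57 / (0.57 + 0.43 × 0.8) = 62.4%, a shift of +5.4 points. The half-widths are 6.7 at n = 210 (42 + 168, France) and 6.3 at n = 234 (47 + 187, Germany). This would need the early course to be a close marker of eventual response, so it leans high.

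**The case against.** The sentence in Section 4 can be read as saying only that no eligible subject is barred and that participation is voluntary; it does not tell centres to pick. A reader might infer that the Protocol endorses choosing patients who are doing well. It does not. What stands is narrower: the wording leaves the choice open and no other section closes it.

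Mitigation is also real. Section 3 requires details of all patients not enrolled, which on its face includes eligible patients who were not approached, and the reasons listed in Section 3.7 are examples only. Section 4.3.1 discloses selection bias and its direction for response, and Section 6 promises to qualify the results. Non-invitation could therefore be detected if sites log it and local rules allow. It is still neither prevented nor expressly reviewed.

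A reader might also infer that early imaging is known at invitation. The Protocol sets no on-treatment imaging schedule and leaves follow-up to the physician, so that is unsupported, and the point does not need it.

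Finally, the study is descriptive and tests no hypothesis. That limits the consequences, but the estimates themselves are the product here.

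**Conclusion.** The point holds as a design weakness worth correcting. Invitation is discretionary at a time when early tolerance, delays or stopping can be known, and no safeguard in the Protocol requires that all eligible subjects be approached.

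The bias is possible, not demonstrated, and its size cannot be derived because no invitation rates are given. Under the assumption that subjects with a pattern are invited 0.8 times as often as others, a 30% pattern shifts by about 4.5 points, close to the whole-country half-width of 4.5 to 4.8. A reader might infer from this that bias outweighs sampling error throughout. The documents do not support that: the comparison depends on the assumed r and on the pattern being visible at invitation, and discontinuation over 12 months could move much less, by 0.5 to 2.4 points in the example above.

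**What to change.** Four changes to the Protocol:

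1. In Section 4, replace the permissive clause with: *All eligible subjects will be invited consecutively, at the first routine visit at which they meet the eligibility criteria, until the country cap is reached.* Tying invitation to routine visits respects the rule that the study adds none.
2. In Section 3.7, add *eligible, not invited* as a named reason in the existing log.
3. In Section 6, extend the review of refusals to non-invitation.
4. Report the numbers eligible, invited and enrolled, as local rules permit.

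The cost is small. Sites lose discretion over whom to approach and have slightly more log work; there are no new visits or procedures, and treatment decisions are untouched. If the rule is followed, r = 1, this source of bias is removed and the Table 1 half-widths do not change. It does not recover patients who die before they can be asked, which Section 4.3.1 already acknowledges.

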### **Baseline**

After a subject has been enrolled, baseline (before administration of Vectibix® in combination with chemotherapy) data from that subject's medical records will be abstracted onto the eCRF by the investigator, or designee. If the investigator states a preference for paper CRF, then this option will be made available. Baseline values will be considered as those obtained most recently prior to initiation of Vectibix® in combination with chemotherapy. Baseline data will include the following (where available and recorded as standard clinical practice):

- Physician's speciality
- Type of centre and treatment setting (inpatient vs outpatient)
- Number of cancer patients treated per year by centre
- Date and confirmation of written informed consent, where applicable by local regulations
- Subject demographics: sex, age
- Medical history: all significant co-morbidities, including information on cardiac, respiratory, metabolic function
- SADRs and ADRs to Amgen product
- Subject metastatic colorectal cancer (mCRC) history:
  - Date of primary CRC and date of metastasis diagnosis
  - Site of primary tumour: rectum vs. colon, right vs. left colon
  - Synchronous vs metachronous mCRC
  - Sites of metastatic disease: liver, lung, other
  - Number of metastases overall and lesions by site
  - Tumour related symptoms (eg, pain, discomfort)
- Prior treatment history for CRC
  - All prior treatments for CRC and/or mCRC management including surgical procedures, radiotherapy, chemotherapy, biological therapy and/or other systemic anticancer therapy including initial Vectibix® plus chemotherapy infusions, other procedures, and dates of relapse and progression
- Subjects treatment goal
- Resection status
- Method and date of *KRAS* testing, if available. Data on other biomarkers, if conducted, will also be collected.
- ECOG performance status

- 
- Physical examination (abbreviated) including height, body weight.  
**The following key data will also be collected at baseline where available. This data must be generated prior to the subjects first dose of Vectibix® :**
  - All baseline laboratory tests performed prior to the subject receiving their first dose of Vectibix

#### Follow-up Observation Period

Data obtained after the initiation of Vectibix® in combination with chemotherapy, and subsequently during the remainder of the 12-month observational period will similarly be abstracted onto the eCRF (or paper CRF) based on physician preferences for follow up.

Follow-up data post initiation of Vectibix® treatment will be collected at the next patient visit (based on physician preferences for follow up) throughout the observation period until 30 days after the end of Vectibix® treatment, death, withdrawal of consent, loss to follow-up, or up to 12 months from the first dose of Vectibix®, whichever occurs first.

This data will include the following (where available and recorded as standard clinical practice):

- Vectibix® treatment pattern including:
  - start and stop dates
  - dose and schedule
  - total number of infusions received
  - dose reductions, dose delays, and reasons for dose reductions or delays
  - reason for treatment discontinuation
- Concomitant anticancer therapy for mCRC including surgical procedures, radiotherapy, chemotherapy, biological therapy and/or other systemic anticancer therapy and other procedures. Data to include:
  - type of therapy
  - start and stop dates
  - dose, route, and frequency (if applicable)
  - reason for cessation of therapy
- Tumour response follow up (radiological imaging of sites of disease, investigator's assessment of tumour response)
- Resection status
- Healthcare resource utilization including type of visit (inpatient, outpatient, ER, other) and reason for hospitalisations
- Relevant concomitant medication
- SADRs and ADRs to Amgen product

---

## **End of Observation Visit**

Documentation at the end of observation period is required (defined as completion of 12-month observation period, discontinuation of Vectibix® treatment, death, withdrawal of consent, or loss to follow-up [whichever occurs first]):

- Date and reason for ending study:
  - 12-month observation period reached
  - Discontinuation of Vectibix® treatment – date and reason for ending Vectibix® treatment
  - Death – date and primary cause of death to be recorded
  - Loss to follow-up
  - Withdrawal of informed consent
- Planned anti-cancer treatments initiated post Vectibix® discontinuation
- SADRs and ADRs to Amgen product

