#### **End of Observation Visit**

Documentation at the end of observation visit is required (defined as completion of 12-month observation period, death, withdrawal of consent, or loss to follow-up; whichever occurs first):

- Date and reason for ending study:
  - 12-month observation period reached
  - Discontinuation of Vectibix® treatment – date and reason for ending Vectibix® treatment
  - Death – date and primary cause of death to be recorded
  - Loss to follow-up
  - Withdrawal of informed consent
- Planned anti-cancer treatments initiated post Vectibix® discontinuation
- SADRs and ADRs to Amgen product

---

**Statistical Considerations:** The analysis of this study will be descriptive in nature. The data will be summarised for mCRC subjects with wild-type *KRAS* status who received Vectibix® as first-line treatment in combination with FOLFOX and separately for subjects who received Vectibix® in combination with FOLFIRI as second-line treatment in subjects who have received first-line fluoropyrimidine-based chemotherapy (excluding irinotecan). The data will be summarized by country. Selected sensitivity analyses may be performed if appropriate. For continuous outcomes, the mean, standard deviation, median, and range will be provided. For categorical variables, the frequency and percentage will be displayed. The percentage with two-sided 95% CI for the treatment pattern of Vectibix® (eg, cumulative proportion (over specified time period) of subjects with Vectibix® dose change) will be calculated. Duration of exposure, total number of infusions received, and the chemotherapy combined with Vectibix® will be summarized.

**Rationale:** The data being collected is to anticipate expected reimbursement agency requirements in Germany and France. The requirements focus on gaining a clear understanding of the real life use of Vectibix® in accordance with the new label, and so the objectives in this study have been defined to meet such requirements. This study will thus be conducted to gain understanding of Vectibix® use for the treatment of subjects with wild-type *KRAS* mCRC, in first-line in combination with FOLFOX or second-line in combination with FOLFIRI in routine clinical practice.

Figure 1. Sample Selection Flowchart

[figure not shown]
[figure not shown]

Figure 2. Study Design and Follow-up Schema

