## Glossary

Abbreviation or Term	Definition/Explanation
5-FU	5-fluorouracil
ADR	Adverse drug reaction
BSC	Best supportive care
CI	Confidence interval
CRC	Colorectal cancer
CRO	Contract Research Organisation
CRF	Case report form
CT	Computerized tomography
DRG	Diagnosis related group
ECOG	Eastern Cooperative Oncology Group
EOO	End of observation
eCRF	Electronic case report form
EGF	Epidermal growth factor
EGFR	Epidermal growth factor receptor
EDC	Electronic data capture
ELISA	Enzyme-Linked Immunosorbent Assay
ER	Emergency room
FLFAS	First Line Full Analysis Set
FOLFOX	FOL (Folinic acid, Leucovorin) F (Fluorouracil – 5FU) OX (Oxaliplatin)
FOLFIRI	FOL (Folinic acid, Leucovorin) F (Fluorouracil – 5FU) IRI (Irinotecan)
ICH GCP	International Conference on Harmonization Good Clinical Practice
ICU	Intensive Care Unit
IEC	Independent ethics committee
IFL	Irinotecan, leucovorin (folinic acid), and fluorouracil
KRAS	Kirsten rat sarcoma viral oncogene homolog
mCRC	Metastatic colorectal cancer
MRI	Magnetic resonance imaging
NCI-CTC	National Cancer Institute Common Terminology Criteria
OS	Overall survival
PFS	Progression-free survival
RECIST	Response Evaluation Criteria In Solid Tumours
SADR	Serious adverse drug reaction
SLFAS	Second Line Full Analysis Set

Abbreviation or Term	Definition/Explanation
SmPC	Summary of Product Characteristics
VEGF	Vascular Endothelial Growth Factor
Source Data	Information from an original record or certified a copy of the original record containing patient information for use in observational research. The information may include, but is not limited to observations necessary for the reconstruction and evaluation of the study. Source data are contained in source documents (original records or certified copies). Examples of source data include Subject ID.
Study day 1	Defined as the first day that Vectibix® was administered in combination with chemotherapy to the subject in routine clinical practice
End of observation (EOO) for individual subject	Defined as the last day that protocol-specified observation data is collected for an individual subject. Subjects will be followed-up until approximately 30 days after the end of Vectibix® treatment, death, withdrawal of consent, loss to follow-up, or up to 12 months from the first dose of Vectibix®, whichever occurs first. This will also mark the end of study for a subject.

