### **3.3.2 End of Study**

The end of the study for an individual subject is defined as the last day that protocol-specified observation data is collected for an individual subject. Subjects will be followed-up until approximately 30 days after the end of Vectibix® treatment, death, withdrawal of consent, loss to follow-up, or up to 12 months from the first dose of Vectibix®, whichever occurs first.

The end of study is defined as when the last subject is followed-up for the purposes of final collection of observation data. The study will end when the last subject remaining on the study either completes the 12-month observation period, dies, withdraws informed consent, or is lost to follow-up, whichever occurs first.

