#### **7.1.2 Reporting Procedures for Adverse Drug Reactions**

Data on suspected ADRs will be collected and reported in this study but not adverse events that are not considered related to Amgen medicinal product.

---

The investigator is responsible for ensuring that any suspected ADRs observed by the Investigator or reported by the subject are documented in a subject's medical record as possibly related to an Amgen medicinal product, and that those occurring between baseline and the end of observation visit are reported using the applicable form (eg, ADR Summary CRF) within 30 calendar days of discovery or notification.

The investigator must assign the following ADR attributes:

- ADR diagnosis or syndrome(s), if known (if not known, signs or symptoms),
- Dates of onset and resolution,
- Severity,
- Assessment of relatedness to Vectibix®, and
- Action taken.

The investigator may be asked to provide follow-up information on the reported adverse drug reaction.

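### The two End of Observation Visit definitions contradict the protocol's own 30-day rule, so adverse drug reaction reporting could close up to 30 days apart between sites

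*Protocol*

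**What the plan says.** **The recurring rule.** The glossary fixes when observation of one person stops: "Subjects will be followed-up until approximately 30 days after the end of Vectibix® treatment, death, withdrawal of consent, loss to follow-up". The remaining limit is 12 months after first dose, and the earliest event applies. It adds that this is also the subject's end of study. Section 3 describes the third part of the eCRF in the same way: "approximately 30 days after the end of Vectibix® treatment or 12 months from the initiation of Vectibix®, whichever occurs first". The rule also stands in the synopsis (Study Design), Section 3.3.1 and Section 3.3.2. The Follow-up Observation Period text, in the synopsis and in Section 4, uses 30 days without the word approximately.

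**Section 4, End of Observation Visit.** Besides the 12-month limit, observation ends at "discontinuation of Vectibix® treatment, death, withdrawal of consent, or loss to follow-up [whichever occurs first". Discontinuation itself is the trigger.

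**Synopsis, End of Observation Visit.** The same visit is "defined as completion of 12-month observation period, death, withdrawal of consent, or loss to follow-up; whichever occurs first". Discontinuation is absent from the definition, but the list of reasons directly below it includes "Discontinuation of Vectibix® treatment – date and reason for ending Vectibix® treatment".

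**Safety reporting.** For ADRs, Section 7.1.2 says "those occurring between baseline and the end of observation visit are reported using the applicable form". For serious ADRs (SADRs), Section 7.2.2 runs from baseline to the end of the observation period. Neither section states a number of days.

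**Study level.** Section 3.3.2 says: "The study will end when the last subject remaining on the study either completes the 12-month observation period, dies"; withdrawal and loss are the other two routes. The glossary has the same study-level wording. Neither mentions the 30-day end point.

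**The concern.** One event has three written triggers, all in current text. The two outliers are the passages that carry the heading End of Observation Visit, and that visit is the point to which ADR reporting runs. A site looking up when its ADR obligation ends is led to a definition that differs from the glossary.

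At stake is a consistent safety-reporting window. Take a reaction first seen between discontinuation and day 30. It is inside the window under the glossary rule and outside it if the Section 4 visit definition is followed. By contrast, Section 7.3 gives pregnancy and lactation monitoring its own limit of 30 days after the last dose; the ADR and SADR sections have nothing equivalent.

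This governs what sites collect and report, so it is a protocol matter. Reactions that were never reported cannot be restored in the analysis.

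**Working it through.** The protocol states no figure that depends on this date, so there is nothing to reproduce. The check sets the definitions side by side and then gives a scale under stated assumptions.

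**1. The three triggers, for a subject who ends Vectibix at month T < 12 and is not lost, withdrawn or dead**

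| Place | End of observation |
|---|---|
| A. Section 4, End of Observation Visit | T |
| B. Glossary; Section 3; 3.3.1; 3.3.2; synopsis Study Design; both Follow-up texts | T + 30 days, capped at month 12 |
| C. Synopsis, End of Observation Visit, definition read alone | month 12 |

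**2. Difference between A and B per subject.** It is the smaller of 30 days and (12 months − T). With 30 days = 30/30.4375 = 0.986 months, the full 30 days applies to anyone stopping before month 12 − 0.986 = 11.01. Later stoppers lose less, and subjects still on treatment at month 12 lose nothing. The maximum is 30 days.

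**3. How many subjects it touches (assumption, not a protocol figure).** Let time to the end of Vectibix be exponential with median m, with no death or loss, so λ = ln 2 / m. The share stopping before month 12 is 1 − exp(−12λ). As rough proxies for m, use the pivotal-study PFS medians in Section 2.2.2 (10.0 months first line, 6.7 months second line), plus 4 months as a low case.

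- m = 10.0: 56.5%
- m = 6.7: 71.1%
- m = 4: 87.5%

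With the 60/40 split of lines in Section 5.3: 0.60 × 56.5% + 0.40 × 71.1% = 62.3%, and 740 × 0.623 ≈ 461 subjects. Across the whole range: 740 × 0.565 ≈ 418 to 740 × 0.875 ≈ 648.

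**4. Mean observation time under A and B, same assumptions.** Mean A = (1 − exp(−12λ))/λ. Mean B = d + (1 − exp(−λ(12 − d)))/λ, with d = 0.986.

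- m = 10.0: 8.15 and 8.69 months, difference 0.54
- m = 6.7: 6.87 and 7.56 months, difference 0.69
- m = 4: 5.05 and 5.90 months, difference 0.85

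At 30.4375 days per month this is about 16 to 26 days per subject, averaged over all subjects. It is the gap between a site that always follows A and one that always follows B, not an expected loss for the study.

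**5. What does not move.** Section 5.6.2.1 builds cumulative dose, maximum dose, number of infusions and duration of exposure from infusions up to the last one. The 30 days after the end of treatment add nothing to them. Table 1 depends only on numbers of subjects and assumed proportions.

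**The case against.** The strongest reply is that one rule plainly governs. The glossary defines the term formally, the rule is repeated throughout, and the visit passages read as loose shorthand introducing a list of reasons. More specifically, the Follow-up Observation Period text comes directly before the visit text in both the synopsis and Section 4. It sets a limit of 30 days after the end of Vectibix and lists ADRs, SADRs, response, resection status and resource use under it. A careful site would collect reactions to day 30.

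This stands in part. It shows which text is out of line, and it rules out saying that Section 4 as a whole discards the post-treatment window. It does not remove the conflict, because Section 7.1.2 points to the visit and both visit definitions are wrong against the glossary. The serious-reaction window is less exposed, since it refers to the period; but Section 4 also words its definition as one of the period.

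Three stronger readings are tempting, and the document does not support them:

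- **Early stoppers stay under observation to 12 months.** The synopsis definition says so only if read alone; its reason list and the follow-up text before it say otherwise. The end-of-study rule concerns the last subject still on study, and Section 3.3.2 gives the 30-day rule for individuals first. Mentions of a 12-month observation period in Section 3.3.1 and in the Section 4 follow-up text are loose wording.
- **Resections and later therapy are under-counted, so a 12-month chart look-up is needed.** The outcomes are documented conversion to resectability and planned later treatment. The interval from last dose to surgery is not given. A look-up would be new data collection after the subject's defined end of study.
- **Person-time denominators are distorted.** Sections 5.6.1 and 5.6.2 plan no person-time rates.

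**Conclusion.** The contradiction is real and of moderate weight. The protocol's dominant rule is 30 days after the end of Vectibix, or 12 months; neither End of Observation Visit definition matches it, and the two do not match each other. The supported consequence is limited to the closing date for ADR reporting and, less directly, SADR reporting: up to 30 days' difference between sites for subjects who stop before month 12.

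The 30-day maximum follows from the text, taking discontinuation and end of treatment as the same date. The share of subjects affected does not: 56.5% to 87.5% rests on an assumed exponential time on treatment with a median of 4 to 10 months and no death or loss. How many sites would follow which wording is unknown. The study is descriptive, safety is not a listed objective or outcome, and the Vectibix exposure results do not depend on the point. It should be corrected, but it does not threaten the study's primary purpose.

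**What to change.** - Reword the End of Observation Visit definition in the synopsis and in Section 4 to agree with the glossary definition for an individual subject, keeping its term, end of Vectibix treatment. Replacing that term with last dose could close a subject during a dose delay.
- State in Sections 7.1.2 and 7.2.2 that both reporting windows end on that same date, and use one term for it in place of visit in one section and period in the other.
- Align the study-level end wording in the glossary and Section 3.3.2, so that it allows for the last subject leaving by the 30-day route.
- Use either 30 days or approximately 30 days throughout.

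If the sponsor intends a different cut-off, it must be stated identically in all these places. The cost is amendment wording and a note to sites; no visit, procedure or extra record abstraction is added.
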